#### MODE DE STERILISATION

Dispositif stérile à usage unique. Stérilisé par irradiation gamma. Ne pas restériliser.

#### CONSERVATION

Conditions de stockage recommandées : température ambiante.

Ne pas utiliser le dispositif au-delà du dernier jour du mois d'expiration figurant sur l'étiquette.

A réception du dispositif, s'assurer que le conditionnement n'a été ni ouvert ni endommagé et conserve intègre son scellage. Ne pas utiliser le dispositif si l'emballage présente un défaut d'intégrité pouvant compromettre la stérilité.

#### TRACABILITE

Une étiquette de traçabilité identifiant le type et le numéro de lot du dispositif est jointe à chaque emballage de dispositif. Cette étiquette est destinée à être collée sur le dossier médical permanent du patient afin de clairement identifier le dispositif implanté.

Marquage CE initial: 2014

Do not use if package is opened or damaged. / Ne pas utiliser en cas d'endommagement ou d'ouverture de l'emballage.

**STERILE R**

Single use

**Rx  
ONLY**

Do not  
resterilize

Caution, consult  
accompanying  
documents

**CE**  
0459

© 2013 Covidien.

 Sofradim Production, [name].

[www.covidien.com](http://www.covidien.com)

COVIDIEN, COVIDIEN with logo, and Covidien logo and Positive Results for Life are U.S. and internationally registered trademarks of Covidien AG. Other brands are trademarks of a Covidien company, TM brands are trademarks of their respective owner.

Made in France. 2014/02 - 2

[figure not shown]

# Symbotex™

## Composite Mesh

1074069

EN

### BEFORE USING PRODUCT, READ THE FOLLOWING INFORMATION THOROUGHLY.

#### IMPORTANT!

This booklet is designed to assist in using this product. It is not a reference to surgical techniques. This device was designed, tested and manufactured for single patient use only. Reuse or reprocessing of this device may lead to its failure and subsequent patient injury. Reprocessing and/or resterilization of this device may create the risk of contamination and patient infection. Do not reuse, reprocess or resterilize this device.

#### DESCRIPTION

Symbotex™ composite mesh is made out of a three-dimensional monofilament polyester textile, which is covered with an absorbable, continuous and hydrophilic film on one of its sides. This film is made up of a mix of collagen from porcine origin and glycerol. The collagen film is essentially degraded in less than 1 month.

Non-absorbable pre-placed sutures are tied to the three-dimensional mesh.

A dyed monofilament polyester (D&C Green No. 6) marking is positioned on the center of the textile, on the opposite side of the film, and helps center and orient the mesh.

#### INDICATIONS

Symbotex™ composite mesh is intended for the reinforcement of abdominal wall soft tissue where a weakness exists, in procedures involving primary abdominal wall and incisional hernia surgeries.

The non-absorbable three-dimensional polyester mesh provides long term reinforcement of soft tissues. On the opposite side, the absorbable hydrophilic film minimizes tissue attachment to the mesh in case of direct contact with the viscera.

#### CONTRAINDICATIONS

- As Symbotex™ composite mesh will not stretch to accommodate growth, its use is not appropriate in patients in a period of growth.
- Any foreign material may potentiate or prolong infection in the presence of bacterial contamination, and as such, the use of Symbotex™ composite mesh is not appropriate in an infected or contaminated site. Furthermore, this product should be used with the understanding that infection may require removal of the device.

#### POSSIBLE COMPLICATIONS

The possible complications associated with the use of Symbotex™ composite mesh are those typically associated with surgically implantable mesh: seroma, hematoma, recurrence, adhesions, fistula formation, infection, inflammation, chronic pain, and/or allergic reactions to the components of the product.

Potential events associated with state of the art mesh with similar indication may include: organ injury (including bowel and visceral injury), trocar-site herniation, bowel obstruction and urinary retention (related with the use of anesthetics).

#### WARNINGS

1. To avoid injury, exercise caution if fixating the device in the presence of nerves or vessels.
2. In order to maintain the elasticity and the porosity of the reinforcement, it is recommended that the mesh should not be overly stretched when it is being put in place. A moderate and equal tension should be applied in all directions for fixation in order to account for wound shrinkage during the healing process.
3. Particular attention should be paid not to cut the green marking. It may no longer be centered and lose its functions if the mesh is trimmed.
4. The effectiveness and safety related to the use of this device in pregnant women have not been established. For women planning future pregnancies, the surgeon should be aware that this product will not stretch significantly as the patient grows.
5. The device is provided in a sterile packaging. The packaging is to be checked for any damage before use. Do not use the mesh if the packaging is opened or damaged.
6. The device is provided in a double sterile packaging. It is recommended to open the last packaging only for the placement of the mesh and to handle the latter using clean gloves and instruments.

#### PRECAUTIONS

Users should be familiar with surgical procedures and techniques involving the use of surgical mesh before employing this device.

This device should only be used by experienced practitioners who do so under their own responsibility.

### 1 SCHEMATIC VIEW

- A) GREEN COLORED POLYESTER MARKING
- B) THREE-DIMENSIONAL MONOFILAMENT POLYESTER TEXTILE
- C) FILM MADE OF COLLAGEN AND GLYCEROL

#### OPERATING STEPS - POSITIONING

1. Symbotex™ composite should be hydrated in its original blister before being handled. This is carried out by immersing it completely in a sterile saline solution for several seconds to ensure its conformability and flexibility.
2. When putting it in place, it is essential to perfectly differentiate the film side from the porous textile side in order to situate the device correctly: the porous textile side is placed against the wall for tissue integration while the film side is facing the structures on which the tissular attachment is to be limited.
3. The green marking is then placed against the abdominal wall. It should be visible through the composite mesh. The circular portion of the marking should be centered on the defect, while the triangular portion shall indicate the orientation of the mesh in order to correctly align it to the medial line of the body.
4. Should it be used in a laparoscopic approach, Symbotex™ composite mesh is to be rolled after hydration, with the film facing the inside. The film is then protected when inserted in the trocar.
5. The pre-placed sutures are positioned on the textile side to help with the mesh handling once it is unrolled in the abdominal cavity. These yarns allow to easily pinpoint the mesh textile side. They can be used for the transperitoneal fixation of the mesh.

6. The edge of the reinforcement should be at least 5 cm over the edges of the defect(s). The technique used to anchor the mesh (suture or staples) is left up to the practitioner. It is suggested to fixate the mesh at a distance of approximately 1 cm from the edge of the mesh.

7. Symbotex™ composite mesh can be trimmed to the desired size without impairment to the minimizing tissue attachment properties of the film.

**NOTE: The green textile marking should not be cut. It may no longer be centered and could lose its functions if the mesh is trimmed.**

#### STERILIZATION TECHNIQUE

Sterile single-use device. Sterilized by gamma radiation. Do not re-sterilize.

#### STORAGE

Recommended storage conditions: room temperature.

Do not use the device past the last day of the labeled month of expiration.

Upon receipt of shipment, ensure that the packaging is not open or damaged and retains its sealed integrity. Do not use the device if the integrity of the packaging appears compromised.

#### TRACEABILITY

A traceability label is attached to every device package which identifies the type and lot number of the device. This label should be affixed to the patient's permanent medical record to clearly identify the device which was implanted.

FR

## Renfort Composite

### AVANT D'UTILISER CE PRODUIT, LIRE ATTENTIVEMENT LES INFORMATIONS CI-DESSOUS.

#### IMPORTANT !

Cette notice est destinée à faciliter l'utilisation de ce produit. Elle ne constitue pas une référence en matière de techniques chirurgicales. Ce dispositif a été conçu, testé et fabriqué pour un usage chez un seul patient. Sa réutilisation ou son retraitement peut provoquer un dysfonctionnement et des blessures chez le patient. Son retraitement et/ou sa restérilisation peuvent entraîner un risque de contamination et d'infection du patient. Ne pas réutiliser, retraiter ou restériliser ce dispositif.

#### DESCRIPTION

Le renfort Symbotex™ composite est constitué d'un textile tridimensionnel en polyester monofilament recouvert sur une face, par un film hydrophile, continu et résorbable à base de collagène d'origine porcine et de glycérol. Le film de collagène est essentiellement résorbé en moins d'un mois.

Des fils de suture pré-placés, non résorbables, sont accrochés au renfort tridimensionnel.

Un marquage en polyester monofilament de couleur verte (D&C Green No. 6) est placé au centre du textile, sur la face opposée du film, et aide à centrer et à orienter le renfort.

#### INDICATIONS

Le renfort Symbotex™ composite est utilisé pour le renforcement des tissus mous de la paroi abdominale en présence d'une faiblesse, dans les procédures chirurgicales impliquant les hernies primaires de la paroi abdominale et les hernies incisionnelles.

Le renfort en polyester tridimensionnel non résorbable permet le renforcement à long terme des tissus mous. Sur la face opposée, le film hydrophile résorbable réduit les phénomènes d'adhérence pouvant survenir entre la prothèse et les tissus en cas de contact direct avec les viscères.

#### CONTRE-INDICATIONS

- Comme le renfort Symbotex™ composite ne s'allongera pas avec la croissance, son utilisation n'est pas appropriée chez les patients en période de croissance.
- Tout matériau étranger est susceptible de provoquer ou de prolonger une infection en présence d'une contamination bactérienne et, de ce fait, l'utilisation du renfort Symbotex™ composite peut ne pas convenir en cas d'intervention en site infecté ou contaminé. De plus, ce produit doit être utilisé en sachant que l'infection peut nécessiter le retrait du dispositif.

#### COMPLICATIONS EVENTUELLES

Les éventuelles complications associées à l'utilisation du renfort Symbotex™ composite sont celles classiquement associées à l'implantation d'un renfort chirurgical: sérome, hématome, récurrence, adhérence, formation de fistules, infection, inflammation, douleur chronique, et/ou réactions allergiques aux constituants du produit.

L'état de l'art des renforts utilisés conformément à l'indication, établie que les événements suivants peuvent se produire : dommages aux organes (tels que dommages aux intestins et aux viscères), hernies de trocar, occlusion intestinale et rétention urinaire (qui peut se produire lors de l'utilisation d'anesthésiques).

#### AVERTISSEMENTS

1. Pour prévenir toute blessure, une attention particulière est requise lors de la fixation du dispositif en présence de nerfs ou de vaisseaux.
2. Afin de préserver l'élasticité et la porosité du renfort, il est recommandé de ne pas le tendre exagérément au moment de la pose. La tension doit être modérée et équivalente dans toutes les directions pour fixer le renfort afin de tenir compte de la rétraction de plaie lors de la cicatrisation.
3. Une attention particulière doit être apportée pour ne pas découper le marquage vert. En cas de découpe du renfort, il se peut que le marquage ne soit plus centré et ne conserve pas ses fonctionnalités.
4. L'efficacité et la sécurité relatives à l'utilisation de ce dispositif chez la femme enceinte n'ont pas été établies. Pour les femmes en âge de mener une grossesse, le chirurgien doit être attentif au fait que le dispositif ne s'allongera pas de manière significative lors de la croissance survenant lors de la grossesse.
5. Le dispositif est livré sous emballage stérile. Vérifier l'intégrité de l'emballage avant toute utilisation. Ne pas utiliser le dispositif si l'emballage est ouvert ou endommagé.
6. Le dispositif se présente sous double emballage stérile. Il est recommandé de n'ouvrir le dernier emballage qu'au moment de la mise en place du renfort et de manipuler celui-ci à l'aide de gants et d'instruments non souillés.

#### PRECAUTIONS D'EMPLOI

Les utilisateurs doivent être familiers des procédures et techniques chirurgicales impliquant l'utilisation de renforts chirurgicaux avant d'utiliser le dispositif. Ce dispositif est réservé aux praticiens spécialistes qui l'utilisent sous leur seule responsabilité.

### 1 VUE SCHEMATIQUE

- A) MARQUAGE VERT EN TEXTILE POLYESTER
- B) TEXTILE TRIDIMENSIONNEL POLYESTER MONOFILAMENT
- C) FILM À BASE DE COLLAGÈNE ET DE GLYCÉROL

#### INTERVENTIONS - MISE EN PLACE

1. Avant toute manipulation, le renfort Symbotex™ composite doit être hydraté dans son emballage d'origine par immersion complète, quelques secondes dans une solution physiologique stérile afin de restituer au renfort sa conformabilité et sa souplesse.
2. Au moment de la mise en place, il est indispensable de repérer parfaitement la face du film de la face poreuse du textile, de façon à correctement l'orienter : la face poreuse du textile contre la paroi pour une intégration tissulaire / la face du film en regard des structures pour lesquelles on souhaite limiter les adhérences tissulaires.
3. Le marquage vert est placé contre la paroi abdominale. Il devrait être visible à travers le renfort composite. La partie circulaire du marquage sera centrée sur l'orifice, la partie triangulaire devra être alignée par rapport à la ligne médiale du corps.
4. Dans le cas d'une utilisation par voie laparoscopique, le renfort Symbotex™ composite doit être roulé après hydratation, face film orientée vers l'intérieur, de façon à protéger le film lors du passage dans le trocar.
5. Les fils de couleur placés sur la face textile aident à la manipulation du renfort une fois déroulé dans la cavité abdominale. Ces fils permettent de repérer plus facilement la face textile du renfort. Ils peuvent servir à la fixation transpéritéale du renfort.
6. Le renfort doit déborder d'au moins 5 cm les berges du ou des orifice(s). La technique de fixation du renfort (sutures ou agrafes) est laissée au choix du praticien. Il est recommandé de fixer le renfort à une distance d'environ 1 cm du bord du renfort.
7. Le renfort Symbotex™ composite peut être découpé à la taille désirée, sans perte de la propriété de minimisation des adhérences du film.

**NOTE : Le marquage vert ne devra pas être découpé. En cas de découpe du renfort, il se peut que le marquage ne soit plus centré et ne conserve pas ses fonctionnalités.**

#### MODE DE STERILISATION

Dispositif stérile à usage unique. Stérilisé par irradiation gamma. Ne pas restériliser.

#### CONSERVATION

Conditions de stockage recommandées : température ambiante.

Ne pas utiliser le dispositif au-delà du dernier jour du mois d'expiration figurant sur l'étiquette.

A réception du dispositif, s'assurer que le conditionnement n'a été ni ouvert ni endommagé et conserve intègre son scellage. Ne pas utiliser le dispositif si l'emballage présente un défaut d'intégrité pouvant compromettre la stérilité.

#### TRACABILITE

Une étiquette de traçabilité identifiant le type et le numéro de lot du dispositif est jointe à chaque emballage de dispositif. Cette étiquette est destinée à être collée sur le dossier médical permanent du patient afin de clairement identifier le dispositif implanté.

Marquage CE initial: 2014

Do not use if package is opened or damaged. / Ne pas utiliser en cas d'endommagement ou d'ouverture de l'emballage.

**STERILE R**

Single use

**Rx**  
**ONLY**

Do not  
re sterilize

Caution, consult  
accompanying  
documents

**CE**  
0459

© 2013 Covidien.

 Sofradim Production, [name].

[www.covidien.com](http://www.covidien.com)

COVIDIEN, COVIDIEN with logo, and Covidien logo and Positive Results for Life are U.S. and internationally registered trademarks of Covidien AG. Other brands are trademarks of a Covidien company, ™ brands are trademarks of their respective owner.

Made in France. 2014/02 - 2

## **APPENDIX C**

### **Quality of Life and patient satisfaction Questionnaire**

#### **➤ At 1 month (D30 Follow up)**

##### **1- Do you currently feel post-operative discomfort?**

- No
- Discomfort
- “Pins and needles”
- Loss of sensation
- Moderate pain
- Severe pain
- Other symptoms (please specify)

##### **2- Where are these symptoms located?**

- Several possible answers:
- Operated side
- Scar region
- Other side
- Both sides
- Elsewhere (specify)

##### **3- When exactly do you feel these symptoms?**

- Several possible answers:
- During lifting, coughing or pushing
- During others types of effort (please specify)
- After physical effort or and the end of the day
- At any other particular time (please specify)
- At any time

##### **4- How often do you feel them?**

- Rarely
- several time a week
- Several time a day
- Throughout the day
- 24/24h

##### **5- The symptoms felt:**

- Do not hinder your activities
- Allow you to pursue your activities but at a slower pace

- Cause temporary interruption in your activities
- Prevent certain activities (which one?)

## **6- These symptoms**

- Are more of a nuisance than those of the hernia you previously had
- Are less of a nuisance than those of the hernia you previously had

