One hundred patients will be followed using the online database for registration and patient outcome measurements, including pre-operative, operative, discharge, post-operative course (D1 and D8 follow up), 1 month (D30 follow up), 1 Year and 2 Year follow up. The pain nurses will carry out the pain evaluation on the day of surgery (D0) and on postoperative day 1 (D1) (by phone call in case of day surgery). Pain on day 8 is assessed either during clinical exam or by phone if the patient is already discharged. Patients will be given an appointment for a clinical visit on day 30 (D30 follow up). The post-operative visit at 1 month (D30 follow up) is the standard of care for patient follow up following primary abdominal wall and incisional hernia surgeries.

For long-term follow up, two sets of self-administered QOL questionnaires will be administered by phone call at 1 Year and 2 Year follow-up.

Follow up by phone questionnaires will be performed by a Clinical Research Associate mandated by Club Hernie, independent from the operative surgeons

The Clinical Research Associate will enter into the database answers from the patient-based self-assessment questionnaires.

The answers will be registered without any medical adjustment into the database. The patients who complain of any trouble will be invited to have a clinical visit at the surgeon's office. The correlation between the patient's answer and clinical assessment and physical examination will then be determined.

A patient will be considered lost to follow-up after 5 failed attempts of meticulous postal reminders and phone calls at various times, therefore minimizing the non-response bias.

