### **5.1 Preoperative data**

- Demographic data (age, gender, ASA score, BMI, patient's occupation)
- Relevant prior medical/surgical history (previous surgical procedure including Hernia antecedents and abdominal surgical history) and comorbidities
- Hernia symptoms, disorders, region, discomfort and frequency

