### **5.2 Operative data (D0)**

- Date of surgery
- Surgical technique approach
- Defect size, Hernia type and location
- Mesh size and type (SYM, SYMF; SYMOS)
- Amount of Overlap
- Type of fixation
- Operative time (from incision to closure, skin to skin), ,
- Mesh positioning and time

- Peri-operative events (including SAEs)
- Surgeon satisfaction (Mesh handling, mesh manipulability, ease of use)
- Pain assessment measured with VAS\* score (The pain nurse will carry out the pain evaluation)

\* VAS: The postoperative pain is assessed using a 0–10 Visual Analogue Scale.

Worst pain experienced over the last 24 hours.

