### **5.6 1 month (D30) Follow up**

- Pain assessment measured with VAS\* score
- \* Mid pain for VAS score between 0 and 3; Moderate pain for VAS score > 3 and < 6 ; Severe pain for VAS scores > 6.
- Post-operative complications (including SAEs)
- Quality of Life « QoL » Questionnaire (Appendix C)

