### **Statistical Analysis Plan Summary**

The analysis will be performed for primary and secondary endpoints, all data will be analyzed, according to the methods previously described in the general considerations section.

- 1) Descriptive Analysis of patients registration and outcomes measurement
- 2) Baseline and Demographic Data Analysis
- 3) Operative Data Analysis
- 4) Primary endpoints measured within 1month, 1 Year and 2 Year follow-up
  - a. Peri-operative complications
  - b. Post-operative complications such as anticipated device related complications as pain, recurrence, complications related to adhesions, wound complications, other postoperative complications, SAEs...
  - c. All complications
- 5) Secondary endpoints analysis during the whole follow-up
  - a. Surgical technique and mesh fixation
  - b. Operative time descriptive analysis
  - c. Ease of use / mesh manipulability assessment by surgeons
  - d. Length of hospital stay analysis
  - e. Quality of life and patient satisfaction analysis
  - f. Surgeon satisfaction

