**8- These symptoms**

- Are more of a nuisance than those of the hernia you previously had
- Are less of a nuisance than those of the hernia you previously had

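### Pain counts in the primary endpoint, but no VAS is taken before surgery and the one before-after question has no answer for unchanged symptoms

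*Protocol*

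**What the plan says.** Section 6.2 of the protocol lists among the primary endpoints "Post-operative complications such as anticipated device related complications as pain, recurrence, complications related to adhesions", measured at 1 month, 1 year and 2 years; section 1.1 says much the same. Quality of life and patient satisfaction are secondary endpoints.

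Before surgery, section 5.1 collects "Hernia symptoms, disorders, region, discomfort and frequency". It lists neither a VAS nor the Appendix C questionnaire.

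The VAS first appears in section 5.2, under operative data for D0: "The postoperative pain is assessed using a 0–10 Visual Analogue Scale". The recall window is given as "Worst pain experienced over the last 24 hours". It is then listed at D1, D8, D30, 1 year and 2 years (sections 5.4 to 5.8). Appendix C is first used at D30.

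Appendix C contains one question that compares the present with the time before surgery. It is item 6 at D30 and item 8 at 1 and 2 years, and its only answers are "Are more of a nuisance than those of the hernia you previously had" and "Are less of a nuisance than those of the hernia you previously had".

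**The concern.** A ventral hernia can itself be painful or uncomfortable, and the protocol recognises this by recording hernia symptoms before surgery. When pain after surgery is then counted as a possible device complication, the reader needs to know how much of it is new or worse. A pain score at D30 or 1 year can belong to a patient who was worse before surgery, to one who was the same, or to one who had no pain. Without a preoperative score on the same scale, these three look alike on the VAS.

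The two-answer question is the only place where patients are asked directly about change. If it has no answer for part of the symptomatic group, the split between better and worse is distorted, and in the long-term data it rests on recall over as much as 2 years.

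This is a matter of what is collected. No analysis plan can recover a score that was not taken or an answer that was not offered.

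**Working it through.** The protocol gives no figure on this point. Its only calculation is the sample size for the recurrence rate (section 6.1): 1.96² × 0.059 × 0.941 / 0.05² = 85.31, rounded up to the stated 86. It has no bearing here.

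**1. Schedule, from sections 5.1 to 5.8**

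| Time | VAS | Appendix C | Other symptom record |
|---|---|---|---|
| Preoperative | no | no | hernia symptoms, site, discomfort, frequency |
| D0 | yes, labelled postoperative | no | – |
| D1, D8 | yes | no | – |
| D30 | yes | yes, with item 6 | – |
| 1 and 2 years | yes | yes, with item 8 | – |

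**2. Can the D0 score serve as a baseline?** No. It is described as postoperative pain, and a 24-hour window ending on the day of surgery may include hours before and after the operation.

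**3. What can the preoperative record support?** It overlaps in topic with Appendix C items 1, 2 and 4 at D30 (discomfort, location, frequency) and with items 3, 4 and 6 at 1 and 2 years. Presence, site and frequency can therefore be compared coarsely within a patient. The protocol does not show whether the answer categories match. Severity on the 0-10 scale cannot be compared.

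**4. How far can the two-answer question mislead?** Take patients with current symptoms who also had symptoms before. Let w, u and l be the true shares that are worse, unchanged and less troubled, with w + u + l = 1. Suppose the worse and less-troubled patients answer correctly. Among unchanged patients, a fraction s skips the question, and of the rest a fraction a ticks less. The recorded share of less is

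P = [l + a(1 − s)u] / (1 − su).

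- All unchanged patients tick less (s = 0, a = 1): P = l + u, too high by u.
- All tick more (s = 0, a = 0): P = l is correct, but the share of more is too high by u.
- All skip (s = 1): P = l/(1 − u), too high by l·u/(1 − u). Since l ≤ 1 − u, this is at most u.

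In general P − l is never negative and never exceeds u. The protocol gives no value for u, so the following is an assumed range:

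| u (assumed) | All tick less | All skip |
|---|---|---|
| 10% | 10 points | 0.10/0.90 × l = 0.111 l, at most 10 points |
| 20% | 20 points | 0.20/0.80 × l = 0.25 l, at most 20 points |
| 30% | 30 points | 0.30/0.70 × l = 0.429 l, at most 30 points |

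Patients with current symptoms but none before surgery are outside this calculation. The question asks them to compare with something they did not have. If they tick more, new symptoms are merged with worsened ones; if they skip, they drop out of the comparison.

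**The case against.** The strongest reply is that the registry does not set out to estimate change from baseline. It is a single-group descriptive study of complication incidence, sized on recurrence, and no section promises a pain improvement or a better/worse split as an endpoint. That is true, and it is why this is an improvement to the design rather than a misstated analysis. It does not remove the difficulty of interpreting pain as a device-related complication when its level before surgery is unknown.

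A reader might infer that pain after the mesh cannot be separated from earlier symptoms at all. The documents do not support that: section 5.1 records symptoms before surgery, and step 3 shows what this allows.

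A reader might also infer that symptom-free patients are forced to choose a side. They are not. They answer no at item 1 (item 3 at 1 and 2 years), and the comparison question, which refers back to those symptoms, does not apply to them. A blank from them is expected.

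Two further points have some weight. At 1 and 2 years, patients who report trouble are invited to a clinical visit where complications and VAS are recorded (sections 5.7 and 5.8), so late pain is not judged from the two-answer question alone. That visit still supplies no preoperative score. Also, the data sit in a database shared by all society members, and section 7 rules out specific examinations or laboratory tests beyond usual practice. A single pain score adds neither a visit nor a laboratory test, but it is extra data collection and the shared form must be edited.

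**Conclusion.** The point holds in a limited form. Pain is a named component of the primary endpoint without a preoperative VAS, so change in severity, and pain newly arising or worsened after mesh, cannot be quantified on that scale. The comparison question gives no accurate answer to symptomatic patients who are unchanged or who had no symptoms before.

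The size of the second problem is bounded, not known. The percentage answering less can be too high by up to the unchanged share among symptomatic responders. The 10 to 30 points follow from an assumed share of 10 to 30% and from the least favourable behaviour of those patients. They should not be read as an expected error, nor as an error among all registered patients.

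Recurrence, the sample size and the counting of other complications are untouched. This is a cheap improvement that makes the pain results interpretable; it does not invalidate the registry.

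**What to change.** - Add the 0-10 VAS to the preoperative data in section 5.1.
- Add two answers, *about the same* and *had no symptoms before surgery*, to item 6 (D30) and item 8 (1 and 2 years) of Appendix C.
- Report these items among patients with current symptoms only, with the number who did not answer.
- Describe VAS change from the preoperative score alongside the pain complication rate.

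Repeating the Appendix C questionnaire before surgery is not needed, because section 5.1 already covers much of that content.

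The cost is one score at a preoperative visit that already takes place (section 7.1) and a small edit to the shared database form. Patients already operated on will have no baseline score, so the number with one should be stated.
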